#### 8.3 EXPLORATORY OBJECTIVES

The exploratory objectives of the study were:

# Safety:

- To evaluate changes from baseline to 180 days in:
  - o AEs
  - Clinical laboratory tests (i.e., hematology, fasting clinical chemistry, prolactin, and urinalysis)

Final; 26 Feb 2018 Page 21 of 80

Clinical Study Report: Collaborative Protocol [contact] ClinicalTrials.gov Identifier: NCT02717130

- o Vital signs
- o PSP
- o Injection site reactions (i.e., localized pain, redness, swelling, and induration)
- o EPS:
  - Abnormal Involuntary Movement Scale (AIMS)
  - Simpson-Angus Scale (SAS)
  - Barnes Akathisia Rating Scale (BARS)
- o Columbia Suicide Severity Rating Scale (C-SSRS) for suicidality

Final; 26 Feb 2018 Page 22 of 80

ClinicalTrials.gov Identifier: NCT02717130

## 9 INVESTIGATIONAL PLAN

#### 9.1 OVERALL STUDY DESIGN AND PLAN

This was an open-label, multi-center, longitudinal, within-subject comparison study of the effects of aripiprazole once monthly on 30-, 90-, and 180-day psychiatric re-hospitalization rates following hospital discharge in subjects with schizophrenia compared with prior psychiatric hospitalization rates while on oral antipsychotics.

Prospective subjects underwent screening for eligibility for entry into the study during or immediately after hospitalization for symptoms due to schizophrenia.

An overview of the planned study design is provided in Figure 1.

.

Final; 26 Feb 2018 Page 23 of 80

[figure not shown]

Figure 1 Study Schematic

AE = adverse event, AIMS = Abnormal Involuntary Movement Scale, BARS = Barnes Akathisia Rating Scale, BMI = body mass index, CGI-I = Clinical Global Impression—Improvement, CGI-S = Clinical Global Impression—Severity, C-SSRS = Columbia Suicide Severity Rating Scale, HbA1c = glycosylated hemoglobin, PSP = Personal and Social Performance Scale, REALM-SF = Rapid Estimate of Adult Literacy in Medicine—Short Form, SAS = Simpson Angus Scale, UBACC = University of California, San Diego Brief Assessment of Capacity to Consent

Final; 26 Feb 2018

# 9.1.1 Pre-Screening Assessments

Pre-Screening assessments were conducted to help investigators identify any subjects with literacy or capacity to consent issues prior to study enrollment.

These assessments occurred before the subject entered the Screening Period and gave their written consent via the ICF. Pre-Screening assessments were conducted via the following:

- Rapid Estimate of Adult Literacy in Medicine–Short Form (REALM-SF)
- University of California, San Diego Brief Assessment of Capacity to Consent (UBACC)

# 9.1.2 Screening Period

All recruitment methods conformed to the guidelines of the IRB at the clinical site. The subjects participating in this study had to be capable of understanding the nature of the study. The ICF contained a full description of the procedures and their associated risks. Subjects were given both verbal and written descriptions of the procedures, discomforts, risks, and potential benefits by study personnel. After briefing subjects on the reasons for the research, their rights as a subject, and the risks involved, they were given the opportunity to ask questions. Subjects were asked to paraphrase the ICF. When ready, subjects were asked to give written consent to participate in the study. After the ICF was signed by both the subject and the investigator, each subject was given a copy of the signed ICF. The investigator had full responsibility for all issues pertaining to assent and informed consent. Procedures to be followed when obtaining informed consent are detailed in Section 5.1.

During the Screening Period, subjects could be treated with any oral antipsychotic medication of the clinician's choice, with the exception of clozapine. However, oral olanzapine was permitted during the Screening Period only for subjects who were eligible for Phase A.

Eligibility for the study was determined during the screening period, which could occur at any time, beginning with the first day of hospitalization. Eligibility for the study was assessed via the following:

- Confirmation of a current diagnosis of schizophrenia according to Diagnostic and Statistical Manual, Fifth Edition (DSM-5) criteria
- Review of inclusion and exclusion criteria
- Complete medical history, including demographics, complete psychiatric history including all psychiatric and non-psychiatric hospitalizations and medical interventions occurring within the 6 months prior to the date of signing the ICF:
  - O Data regarding psychiatric and non-psychiatric hospitalizations, including treatment records relevant to determination of study eligibility and identified outcome variables related to ED, outpatient and inpatient treatment episodes as described in the inclusion and exclusion criteria (Section 9.3.1 and Section 9.3.2, respectively) occurring within the 6 months prior to the date of signing the ICF were obtained by searching MO

Final; 26 Feb 2018 Page 25 of 80

HealthNet (Medicaid) and Missouri Department of Mental Health (DMH) data via collaboration with the Missouri Institute of Mental Health (MIMH) or confirmed through all available medical records and reliable data from caregivers. Availability of Medicaid data or documentation of at least one inpatient hospitalization, ED visit, or equivalent (i.e., urgent care center) visit within the previous 6 months of screening was required for eligibility (see inclusion and exclusion criteria, Section 9.3).

- Admission vital signs (e.g., blood pressure, heart rate, respiratory rate, and temperature)
- Admission height, weight, and calculation of BMI
- Admission ECG
- Admission HbA1c, if available
- Admission safety clinical laboratory tests (Section 9.5.1.4.1)
- Admission clinical laboratory results were assessed to rule out exclusionary values (Section 9.3)
- Urine pregnancy test for women of childbearing age
- Previous medications taken within 30 days prior to starting study drug were recorded.
   Concomitant medications including details (e.g., drug name, dose, and frequency) of all current medication(s) and any antipsychotic medications taken within 6 months of screening were recorded.
- The nature of acute hospitalization in this population could indicate prior discontinuation of antipsychotic medications due to noncompliance. Appropriate review of all medications for psychiatric illness, including newly prescribed antipsychotic medication was conducted during screening. Discontinuation or tapering of any psychotropic medication, if deemed clinically appropriate or necessary for those subjects entering Phase A (i.e., Oral Tolerability Phase), started at screening and continued during Phase A.
- Additional clinical laboratory tests (fasting or non-fasting as needed) which were not obtained at admission, were deemed necessary by the PI and/or were required to verify inclusion and exclusion criteria

Fasting or non-fasting clinical laboratory tests that were required to establish eligibility could be performed at any time during the Screening Period. Study specific clinical laboratory tests that required fasting (i.e., fasting lipid profile and fasting glucose) were performed during the Baseline Visit.

Prospective subjects were hospitalized for the necessary length of time as determined by the assigned treatment provider as clinically indicated, per the current SOC. To be eligible, the anticipated duration of hospitalization was to be long enough to accommodate the screening procedures, the 3-day Oral Tolerability Phase (if applicable), and initiation of treatment with

Final; 26 Feb 2018 Page 26 of 80

aripiprazole once monthly. However, some subjects could also enter the study if they were clinically started on long-acting injectable aripiprazole during the hospitalization just prior to study entry.

Following the Screening Period, subjects who had no history of aripiprazole use were entered into Phase A, the Oral Tolerability Phase. Subjects from Phase A that demonstrated tolerability to aripiprazole were then entered into Phase B, the Treatment Phase, where all subjects were treated with long-acting injectable aripiprazole. Subjects who already had a history of tolerating at least three consecutive oral doses of aripiprazole were entered directly into Phase B. All eligible subjects eventually entered Phase B.

# 9.1.3 Phase A – Oral Tolerability Phase

The Oral Tolerability Phase lasted for a minimum of 3 days. Subjects with a history of tolerating aripiprazole (e.g., a history of at least 3 days of oral exposure) were not entered into Phase A; these subjects were entered directly into Phase B following the Screening Phase.

Subjects who met the inclusion and exclusion criteria and had no history of oral aripiprazole use entered Phase A after the Screening Period while still hospitalized. Subjects in Phase A were administered oral aripiprazole, as indicated in the product labeling, to determine tolerability. Dosage was based on symptoms and the judgment of the investigator. The dose of oral aripiprazole could be titrated as needed. Prior antipsychotic medications were tapered off and discontinued during the Screening Period and Phase A as clinically appropriate.

During Phase A, tolerability to oral aripiprazole was evaluated daily for a minimum of 3 days using baseline safety and tolerability measures (i.e., AIMS, BARS, and SAS) either during or closely following completion of oral treatment, in conjunction with clinical judgment. If a subject was unable to tolerate oral aripiprazole, he or she was withdrawn from the study. If the subject showed tolerability to the oral aripiprazole, Phase B baseline/Day 1 occurred with the first aripiprazole once monthly injection given immediately after the Phase B baseline/Day 1 assessments.

Prior antipsychotic medications could be continued or tapered to discontinuation at the investigators discretion based on his or her clinical judgment. Reporting and recording of AEs was completed.

## 9.1.4 Phase B (Treatment Phase)

#### **9.1.4.1** Baseline

Baseline was considered Day 1, or first day of long-acting injectable treatment, of Phase B. However, some subjects could have had their baseline assessments (including any remaining clinical laboratory tests required for screening) performed any time during or immediately after treatment with oral antipsychotic aripiprazole (unless eligible to skip Phase A in which it is any oral antipsychotic), ideally prior to starting long-acting injectable aripiprazole. Participants were allowed, with Principal Investigator approval, to enter the study after starting treatment with long-acting injectable aripiprazole in the hospital and baseline assessments were performed as soon as feasible within 48 hours of hospital discharge.

Final; 26 Feb 2018 Page 27 of 80

Subjects who completed the baseline assessments and met the criteria for inclusion and not for exclusion (Section 9.3.1 and Section 9.3.2) began the Treatment Phase (Phase B).

#### Baseline assessments were:

- Contact from the community support worker (CSW) or study coordinator (SC) via telephone or in-person
- Routine vital signs (e.g., blood pressure, heart rate, respiratory rate, and temperature)
- Height, weight, and calculation of BMI
- Fasting lipid profile (e.g., fasting triglycerides, cholesterol [total, HDL, LDL])
- HbA1c
- Prolactin concentration
- CGI-I
- C-SSRS (Since Last Visit) for suicidality
- AIMS, BARS, and SAS to assess EPS
- PSP
- Injection site reaction assessment (i.e., localized pain, redness, swelling, and induration), if applicable
- AEs and concomitant medications
- Aripiprazole once monthly IM injection plus Day 1 of 14 days of oral aripiprazole, (last baseline procedure), unless subject received injection while hospitalized prior to study entry.

#### 9.1.4.2 Treatment Phase

Eligible subjects who had a history of tolerating oral aripiprazole or were currently taking oral aripiprazole entered Phase B directly from the Screening Period. All other subjects entered Phase B following successful completion of Phase A. After the baseline assessments were completed, the subject received the first aripiprazole once monthly IM injection, in conjunction with the first of 14 doses of concomitant oral antipsychotic medication (see Figure 1). Use of concomitant oral aripiprazole during this lead-in was per the investigator's judgment based on the prescribing instructions.

All subjects must have attended scheduled visits at the Baseline Visit and Weeks 2, 4, 8, 12, 16, 20, and 24, totaling 180 days. Aripiprazole once monthly injections occurred at the Baseline Visit and every 28 (-2, +5) days at Weeks 4, 8, 12, 16, 20, and 24, totaling seven injections. After the

Final; 26 Feb 2018 Page 28 of 80

initial injection of 400 mg, the monthly dosage could be decreased to 300 mg, based on the clinical judgment of the investigator. All aripiprazole once monthly injections were administered based on the investigator's judgment and the prescribing information. For subjects who entered the studies after starting the first dose of long-acting injectable aripiprazole in the hospital, if the initial injection was not 400 mg, the second injection should have been 400 mg, and thereafter, the monthly dose could be decreased to 300 mg, based on clinical judgment of the investigator.

For subjects who were psychiatrically stabilized and discharged prior to the completion of the required 14-day course of oral antipsychotic medication, a pre-discharge assignment was given to a CSW/SC. The CSW/SC maintained regular contact with the subject until the first outpatient visit in Phase B (Week 2), when oral aripiprazole was discontinued. Regular contact was defined as no less than weekly, but could have been more frequent depending on the clinical judgment of the CSW/SC and outpatient treatment team. Following the Week 2 Visit, subjects were to have contact with their assigned CSW/SC based on routine clinical care. Contact with the CSW/SC could be in person or by telephone, as clinically appropriate.

The treating clinician performed a clinical interview and mental status examination based on current clinical standards of care at all outpatient visits, whether scheduled or unscheduled. All episodes of clinical care (i.e., psychiatric and non-psychiatric) were recorded in the source documentation. In addition, the following clinical evaluations were performed as outlined in Table 3:

- Routine vital signs (e.g., blood pressure, heart rate, respiratory rate, and temperature) at each visit
- Height, weight and calculation of BMI at each visit
- Fasting lipid tests [e.g., fasting triglycerides, cholesterol (total, HDL, LDL)]
- HbA1c
- Additional clinical laboratory testing (e.g., hematology, fasting clinical chemistry, prolactin, urinalysis and urine pregnancy test) as described in Table 3 and clinically indicated and determined by treatment team
- AEs and concomitant medications
- CGI-I
- PSP
- C-SSRS (Since Last Visit) for suicidality
- AIMS, BARS, and SAS to assess EPS
- Injection site reaction (i.e., localized pain, redness, swelling, and induration)

Final; 26 Feb 2018 Page 29 of 80

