#### Study Design:

This was an open-label, multi-center, longitudinal, within-subject comparison study of the effects of aripiprazole once monthly on 30-, 90-, and 180-day psychiatric re-hospitalization rates following hospital discharge in subjects with schizophrenia compared with prior psychiatric hospitalization rates while on oral antipsychotics.

Prospective subjects underwent screening for eligibility for entry into the study during or immediately after hospitalization for symptoms due to schizophrenia.

Prospective subjects were hospitalized for the necessary length of time as determined by the assigned treatment provider as clinically indicated, per the current standard of care. To be eligible, the anticipated duration of hospitalization was to be long enough to accommodate the screening procedures, the 3-day Oral Tolerability Phase (if applicable), and initiation of treatment with aripiprazole once monthly.

During the Screening Period, subjects could be treated with any oral antipsychotic medication of the clinician's choice, with the exception of clozapine. However, oral olanzapine was permitted, during the Screening Period only, for subjects who were eligible for Phase A. Following the Screening Period, subjects who had no history of aripiprazole use were entered into Phase A, the Oral Tolerability Phase. Subjects from Phase A that demonstrated tolerability to aripiprazole were then entered into Phase B (i.e., the Treatment Phase, where all subjects were treated with long-acting injectable aripiprazole). Subjects who already had a history of tolerating at least three consecutive oral doses of aripiprazole were entered directly into Phase B. All eligible subjects would eventually enter Phase B. Subjects may also have entered the study if they were clinically started on long-acting injectable aripiprazole during the hospitalization just prior to study entry.

Subjects who met the inclusion and exclusion criteria and had no history of oral aripiprazole use entered Phase A after the Screening Period while still hospitalized. Subjects in Phase A were administered oral aripiprazole, as indicated in the product labeling, to determine tolerability. Dosage was based on symptoms and the judgment of the investigator. The dose of oral aripiprazole could be titrated as needed. Prior antipsychotic medications were tapered off and discontinued during the Screening Period and Phase A as clinically appropriate.

Final; 26 Feb 2018 Page 3 of 80

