AE = adverse events, AIMS = Abnormal Involuntary Movement Scale, ALP = alkaline phosphatase, ALT = alanine transaminase, AST = aspartate transaminase, BARS = Barnes Akathisia Rating Scale, BMI = body mass index, BUN = blood urea nitrogen, CBC = complete blood count, CGI-I = Clinical Global Impression—Improvement, CGI-S = Clinical Global Impression—Severity, C-SSRS = Columbia Suicide Severity Rating Scale, CSW = community support worker, DSM-5 = Diagnostic and Statistical Manual, Fifth Edition, ECG = electrocardiogram, ED = emergency department, HbA1c = glycosylated hemoglobin, HDL = high-density lipoprotein, Hgb = hemoglobin, ICF = Informed Consent Form, LDL = low-density lipoprotein, MO = Missouri, PSP = Personal and Social Performance Scale, SAS = Simpson Angus Scale, SC = Study Coordinator, ULN = upper limit of normal

Note: Baseline was considered Day 1, or first day of long-acting injectable treatment in the hospital, of Phase B. However, some subjects may have had their baseline assessments (including clinical laboratory tests) performed any time during or immediately after treatment with oral antipsychotic aripiprazole (unless eligible to skip Phase A in which it was any oral antipsychotic), ideally prior to starting long-acting injectable aripiprazole. Participants were allowed, with Principal Investigator approval, to enter the study after starting treatment with long-acting injectable aripiprazole in the hospital and baseline assessments were performed as soon as feasible within 48 hours of hospital discharge.

Final: 26 Feb 2018

<sup>a The Oral Tolerability Phase lasted for a minimum of 3 days. Subjects who had history of tolerability (e.g., taking at least 3 consecutive doses) with oral aripiprazole and no history of intolerance could receive their aripiprazole once monthly injection immediately upon completion of the screening procedures. All subjects received the first injection of aripiprazole once monthly at Baseline, Day 1.

b: Discharge could occur at any time after the first injection of aripiprazole once monthly.

<sup>ct The complete psychiatric history included a diagnosis reconciliation form on which information from medical records and a clinical interview by a study clinician were recorded.

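### Section 9.1.4.2 sends current users of oral aripiprazole straight to the depot phase with no minimum number of tolerated doses, a looser rule than the three-dose condition stated elsewhere

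*Combined protocol and SAP*

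**What the plan says.** Phase A is an inpatient oral run-in during which "tolerability to oral aripiprazole was evaluated daily for a minimum of 3 days" (Section 9.1.3). A subject who cannot tolerate the oral drug leaves the study there. Phase B begins with the first once-monthly injection, 400 mg for subjects first injected in the study.

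Five places in the combined protocol and SAP say who may skip Phase A:

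- Synopsis (Study Design) and Section 9.1.2, in identical words: "Subjects who already had a history of tolerating at least three consecutive oral doses of aripiprazole were entered directly into Phase B".
- Section 9.1.3: subjects with a history of tolerating the drug, with three days of oral exposure offered as an example.
- Table 3 footnote a (Section 9.5.2): "Subjects who had history of tolerability (e.g., taking at least 3 consecutive doses) with oral aripiprazole and no history of intolerance could receive" the injection as soon as screening is finished.
- Section 9.1.4.2: "Eligible subjects who had a history of tolerating oral aripiprazole or were currently taking oral aripiprazole entered Phase B directly from the Screening Period". It continues: "All other subjects entered Phase B following successful completion of Phase A".

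Entry to Phase A is also stated from the other side. Section 9.1.2 says: "Following the Screening Period, subjects who had no history of aripiprazole use were entered into Phase A, the Oral Tolerability Phase", and the Synopsis agrees. Section 9.1.3 sends there those who met the entry criteria and "had no history of oral aripiprazole use entered Phase A after the Screening Period while still hospitalized".

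On treatment before either phase, Section 9.1.2 says: "During the Screening Period, subjects could be treated with any oral antipsychotic medication of the clinician's choice, with the exception of clozapine".

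A separate route admits subjects whose clinicians had already begun the injectable in hospital before study entry (Synopsis, 9.1.2, 9.1.4.1). Their injection precedes enrolment, and this point does not concern them.

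**The concern.** Phase A exists to find intolerance while the drug can still be stopped from one day to the next. A monthly depot does not allow that: Section 7.3.3 reports peak concentrations at about 100 hours after a single injection in most subjects. The three-dose condition in the Synopsis and 9.1.2 excuses a subject from Phase A because the same information already exists.

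Section 9.1.4.2 joins two conditions with an *or*. The first is a history of tolerating the drug. The second is simply being on it now. A subject on the first or second dose meets the second condition without the exposure that the Synopsis and 9.1.2 treat as the minimum. Two sites following different sections could handle the same subject differently at a safety step.

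**Working it through.** There is no figure to reproduce. The check is to take one subject at a time, by oral exposure before a first injection given in the study, and read each rule.

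| Oral exposure | Synopsis and 9.1.2 | 9.1.3 | Table 3 footnote a | 9.1.4.2 |
|---|---|---|---|---|
| None | Phase A | Phase A | Direct route not open | Phase A |
| Currently on dose 1 or 2, no earlier tolerated exposure | Neither rule applies | Not clearly placed | Not clearly placed | Phase B directly |
| At least 3 consecutive doses tolerated | Phase B directly | Phase B directly | Phase B directly (if no history of intolerance) | Phase B directly |

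**Middle row, Synopsis and 9.1.2.** The subject has some aripiprazole use, so is outside the Phase A sentence, and has fewer than three doses, so is outside the direct-entry sentence.

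**Middle row, 9.1.3 and footnote a.** The subject is again outside the 9.1.3 Phase A sentence. Three days or three doses is given only as an example, so whether one or two doses amount to a history of tolerability is left open.

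**Middle row, 9.1.4.2.** Current use is enough, and only those remaining go to Phase A. One of the five places therefore clearly places this subject, and it does so in the less cautious direction.

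**Can this subject exist?** Yes. Section 9.1.2 allows any oral antipsychotic except clozapine in Screening, and Section 9.4.5 restricts only clozapine and olanzapine there. Aripiprazole can be newly started. Footnote a adds no waiting time between the end of screening and the injection for direct entrants.

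**Shortfall against the three-dose minimum.** 3 − 1 = 2 doses missing for a subject on dose 1, and 3 − 2 = 1 for a subject on dose 2. Section 7.3.1 describes once-daily oral dosing, so this is 2 or 1 further days. A full Phase A is at least 3 days.

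**The first condition in 9.1.4.2.** It requires a history of tolerating the drug but gives no dose count either, so one or two past doses could be argued to meet it. A repair confined to current use would leave that opening.

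**Safeguards, and whether any sets a minimum oral exposure:**

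- Injections follow investigator judgment and the prescribing information (9.1.4.2, 9.4.1): no minimum is stated in the protocol, and the label is not among the documents.
- Exclusion criterion 4 removes known intolerance: it does not require shown tolerance.
- AIMS, BARS, SAS and adverse events at Screening and Baseline (Table 3), with the injection as the last baseline procedure (9.1.4.1): these are assessments, with no exposure requirement.
- Daily vital signs in hospital (Table 3 footnote i): likewise.

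**The case against.** The best case for the plan has four parts.

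First, injections must follow the labeling and the investigator's judgment, so the label may itself prevent an injection after one dose. This cannot be settled from the documents. It stands as a mitigation, and it means that an injection contrary to labeling is not shown.

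Second, a reader might infer that these subjects would be injected with no tolerability assessment at all. The documents do not support that. The scales that Section 9.1.3 names for tolerability are done at Screening and Baseline on both routes, and adverse events are collected from consent. What is skipped is the daily evaluation over at least three days, together with any minimum exposure.

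Third, every direct entrant skips that daily evaluation, including one with three tolerated doses long ago. This is correct. The difference due to the current-use wording is one or two oral doses in a subject with no earlier tolerated exposure.

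Fourth, a reader might infer that 9.1.4.2 overrides an express ban elsewhere. It does not. The other sections leave this subject unrouted or unclear, and in two of them the three-dose or three-day figure is only an example. The inconsistency remains, because 9.1.4.2 alone accepts current use in place of tolerated exposure.

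**Conclusion.** The point holds as a conflict between a routing sentence and the plan's own safety condition. Under 9.1.4.2, a subject newly started on oral aripiprazole in Screening, with one or two doses and no earlier tolerated exposure, qualifies for the first depot injection. That is one or two doses short of the minimum in the Synopsis and 9.1.2. The existing safeguards reduce the risk, but none puts a minimum oral exposure into the protocol.

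This rests on the protocol text alone and on reading current use to include a start during Screening, which 9.1.2 permits. The documents do not say how many subjects took this route, and they show no harm from it. Sample size, power and alpha are unaffected. The Synopsis reports that the study was terminated for slow enrollment after 9 subjects were recruited, so the correction now matters mainly for the stated rule and for any protocol that reuses this text. It should be made, but it does not invalidate the design.

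**What to change.** Replace both conditions in the 9.1.4.2 sentence with one, for example: *Direct entry to Phase B is for eligible subjects who have tolerated three or more consecutive oral doses of aripiprazole at any time before the first injection, in past or current use, and who have no history of intolerance.*

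Use the same criterion in the Synopsis, 9.1.2, 9.1.3 and Table 3 footnote a, in place of the wording that gives three days or doses only as an example. It must not require current use, or past tolerators not now on the drug would be sent to Phase A, contrary to the Synopsis and 9.1.2.

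Send every subject who does not meet the criterion to Phase A, replacing the sentences in the Synopsis, 9.1.2 and 9.1.3 that reserve Phase A for those with no prior use. Except only subjects already clinically started on long-acting injectable aripiprazole during the current hospitalization, and state that exception wherever the routing is given, including the sentence in 9.1.4.2 on all remaining subjects.

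The cost is a wording change in five places. A few subjects would spend more time on oral drug before injection, possibly as inpatients: 1 or 2 days if Screening continues to the third dose, or at least 3 days for a full Phase A, so about one to three days in all. Already-injected subjects are unaffected.
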